- Clinical assessment: weight, general condition (WHO)
- Evaluation of the tolerance of the previous embolization or chemoembolization
- Biological check-up:
 - CBC-platelets
 - INR, aPTT, creatinine, bilirubin (total, conjugated), AST, ALT, PAL

NB: An abdominal CT scan may be performed if necessary for technical reasons before the 2nd embolization or chemoembolization session. Caution: this imaging should not be used to evaluate the response to treatment of metastases.

Every 3 months (+/- 1 week) from the date of the first embolization or chemoembolization (except DNA and ARC monitoring for positive serology)

- Clinical assessment: WHO, weight, evaluation of side effects
- Bioassay:
 - CBC/platelets, urea and creatinine + calculated creatinine clearance (Cockcroft formula), blood ionogram
 - INR, aPTT, albumin, alkaline phosphatase, AST, ALT, bilirubin (total and conjugated), gamma-GT
 - Serum cholesterol and triglycerides
 - Fasting blood glucose and HbA1c
 - Chromogranin A, urinary 5HIAA
- If HBV positive, monitor DNA approximately every 3 weeks or 6 weeks depending on the result (see Table 2-2)

- If HCV positive, monitor RNA every 6 weeks (see Table 2.3)
- Morphological assessment: triphasic thoracic-abdominal-pelvic CT scan with target measurement according to RECIST V1.1 criteria (Appendix 3). Evaluation CT scans should be performed in the same center as the initial examination

NOTE: Patients whose treatment is temporarily or permanently discontinued due to an adverse event or laboratory abnormality suspected to be related to everolimus should be monitored at least weekly until the adverse event resolves or returns to Grade 1

2. Post-treatment monitoring protocol

- **After discontinuation of treatment for hepatic progression**
 - After hepatic progression, the clinical, biological and morphological monitoring of the patient will be left to the investigator's discretion
- **After discontinuation of treatment for a reason other than hepatic progression**
(e.g. toxicity, extra-hepatic progression, patient's wish, :)
 - Morphological surveillance: CT every 3 months until liver progression occurs, according to the same modalities as the initial morphological evaluation (triphasic thoraco-abdomino-pelvic CT with target measurement according to RECIST V1.1 annex 3)

IX. STOP PROCESSING THE STUDY

The processing of the study will be stopped in case of:

- Investigator's decision

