- Major toxicity requiring discontinuation of treatment (despite protocol adaptations)
- Serious or unexpected event requiring discontinuation of protocol treatment
- Disease progression (hepatic, extra-hepatic, clinical)
- Patient refusal
- Death of the patient

X. CENTRALIZED PROOFREADING OF TDM

To address the primary endpoint of efficacy of everolimus treatment after embolization or chemoembolization, a centralized review of morphological examinations of the inclusion workup and follow-ups will be performed by an independent review committee.

To do this, make a copy of the imaging to be kept in the patient's file. The FFCD CRA in charge of your center will make an anonymized copy of the CD ROM and send the imaging to the FFCD imaging platform.

XI. MANAGEMENT OF SERIOUS ADVERSE EVENTS (SIA)

Security assessment parameters

Safety will be assessed by evaluating the general and clinical condition of the patients and by collecting events occurring between visits during consultations, by regular blood tests. Toxicities will be assessed using the NCI-CTC-AE version 4.0 toxicity scale (see Appendix 4).

Definitions

a. Adverse Event (AE)

An adverse event is a harmful occurrence in a person who is a subject of biomedical research, whether or not the occurrence is related to the research or the product being investigated.

All adverse events will be recorded in the observation book on the pages provided.

b. Serious Adverse Event (SAE)

A serious adverse event is any event that

- Resulting in death,
- Life-threatening,
- Leading to hospitalization or prolonged hospitalization,
- Causing permanent disability or severe temporary incapacity,
- Causing a birth defect, fetal malformation or abortion,
- Medically significant

The terms disability and incapacity correspond to any temporary or permanent physical or psychological handicap, clinically significant and affecting the physical activity and/or quality of life of the patient.

Any clinical event or laboratory result considered serious by the investigator and not corresponding to the severity criteria defined above is considered medically significant. They may put the patient at risk and require medical intervention to prevent an outcome corresponding to one of the above mentioned severity criteria (e.g. overdose, second cancers, pregnancies and new events may be considered as medically significant).

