Pregnancy is an exclusion criterion in this trial. However, if a pregnancy is discovered after inclusion, the patient must be excluded from the trial. The sponsor should be informed without delay via the serious adverse event reporting form (no severity criteria should be checked). The patient should be followed until the outcome of the pregnancy and this outcome, whatever it may be, should be reported to the sponsor.

Hospitalizations included in the protocol will not be considered an SAE.

c. Undesirable Effect

Any noxious and undesired response to an investigational drug at any dose or to any investigational component. The adverse reaction is serious if it meets the severity criteria (see above).

d. Unexpected Serious Adverse Effect

An unexpected serious adverse reaction is an event that is not mentioned, or that differs in nature, intensity, or evolution from the product's reference document (Investigator's Brochure or RCPs).

In this essay the reference documents will be:

- For everolimus, the Summary of Product Characteristics for Afinitor® (Appendix 6)

The versions of the Investigator's Brochure and PCR (used for the definition of expected or unexpected everolimus) will be the latest available on the anniversary date of the start of the trial.

What to do

The investigator informs the sponsor of all Serious Adverse Events (Expected and Unexpected), whether or not attributable to the research, that occur during treatment and within 30 days of the last treatment administration.

All Delayed Serious Adverse Events (occurring after this 30-day period) considered reasonably related to the protocol treatment(s) or research should be reported without time limitation.

The report is made by faxing the "notification of a serious adverse event" form (Appendix 7), documented as precisely as possible, dated and signed, within 24 working hours of their discovery to the **FFCD's Randomization Management Analysis Center (CRGA): by fax to [name]**

Modalities and duration of follow-up of individuals following the occurrence of adverse events

The investigator is responsible for appropriate medical follow-up of patients until resolution or stabilization of the effect or until the patient's death. This may sometimes mean that this follow-up extends beyond the patient's discharge from the trial.

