The description of clinical and medical variables will be done using percentages (95% confidence interval) and mean (standard deviation) and median (Min-Max) as well as the interquartile range (Q1-Q3).

Survivals and times will be estimated by the Kaplan Meier (KM) method. They will be described by medians and rates at different time points with their 95% confidence intervals. Median follow-up time will be calculated using the reverse Kaplan Meir method.

The results for the primary endpoint will also be described by a Water Fall plot representing for each patient the percentage change at 24 months in liver metastasis size since the measurement at inclusion according to the response according to the RECIST V1.1 criteria.

The time to onset of grade 3/4/5 toxicity will be estimated using the Kaplan Meier method.

Exploratory analyses

- research into factors predictive of progression-free survival and/or overall survival
- comparison of progression-free survival between embolization alone and chemoembolization

4. Independent committees

An independent committee will be formed and will include at least: two physicians (oncogastroenterologists), a statistician, a pharmacovigilance expert. The independent committee may meet at any time during the protocol when deemed necessary by the Sponsor.

XIII. JUSTIFICATION OF THE TEST

Neuroendocrine tumors (NETs) are a heterogeneous group of rare tumors. The prevalence of these tumors is estimated to be between 0.4 and 1 per 100,000 inhabitants per year. In the gastrointestinal tract, the most frequent locations are the appendix (19%), the small intestine (15%) and the rectum (11%). Neuroendocrine tumors of the small intestine mainly affect young adults between 30 and 35 years of age, while those of the colon tend to occur around 60 years of age [[1]].

Treatment of digestive endocrine tumors

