7.1.7 Statistics

Quantitative variables will be described using the number, median, mean, standard deviation of the mean, minimum, maximum, and interquartile range (Q1-Q3). Quantitative variables may be categorized using their median or a cut-off known from the medical literature.

Categorical variables will be described using percentages, and if necessary their two-sided 95% confidence intervals (calculated using the exact method).

Missing values will not be included in the calculation of frequencies and percentages.

The **confidence intervals** provided will be two-sided 95% confidence intervals, except for the primary criterion where a one-sided 95% confidence interval will be given.

Survival data will be estimated and plotted using the Kaplan-Meier method (Kaplan and Meier, 1958).

This will be described by the median and rates calculated at different times. Two-sided 95% confidence intervals will be provided. Confidence intervals for the rates will be constructed from the Greenwood variance calculated using the log-log transformation.

The median follow-up time will be calculated using the reverse Kaplan-Meier method (Shemper, 1996).

For uni and multivariate analyses, hazard ratios will be estimated using a Cox model (Cox, 1984). The proportionality of the rates will be tested using the graphical representation and the test based on Schöenfeld residuals (Grambsch, 1994); the linearity of the effect of the continuous variables on the risk will be assessed from the graphical representation of the martingale residuals. Confidence intervals for the coefficient estimates of the Cox models will be calculated using the Wald method.

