7.6.3 ISG

The summary of the SAEs will be provided by pharmacovigilance.

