7.6.4 Toxicities

Population SP

Toxicities (graded according to NCI-CTC v 4.0) will be described by:

- The total number of patients by maximum grade of toxicity (grade 1-2-3-4-5);
- The number of patients and the maximum toxicity grade achieved (grade 1-2-3-4-5) by SOC and type of toxicity;
- Total number of patients by maximum grade of toxicity by grouping grades (grade 1-2 and grade 3-4-5);
- The number of patients and the maximum grade of toxicities achieved by grouping the grades (grade 1-2 and grade 3-4-5) by SOC and type of toxicities.

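### The SAP omits the protocol's time-to-onset analysis of grade 3–5 toxicity without explanation; if restored, it should be a cumulative incidence, because one minus Kaplan-Meier overstates incidence when other deaths come first

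*Protocol*

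**What the plan says.** Protocol XII.3, under Main analyses: "The time to onset of grade 3/4/5 toxicity will be estimated using the Kaplan Meier method". No time origin, censoring rule or competing event is given.

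SAP 7.6.4 describes toxicity by patient counts, starting with "The total number of patients by maximum grade of toxicity (grade 1-2-3-4-5"), then by organ class and type, and with grades grouped as 1-2 and 3-4-5. SAP 5.7.3, which lists the tolerability criteria, has no time to onset. The general statement in SAP 7.1.7 is "Survival data will be estimated and plotted using the Kaplan-Meier method"; toxicity is not named there. Sections 7.5.2 to 7.5.4 apply the method to hepatic progression-free survival, progression-free survival and overall survival only. For serious events, SAP 7.6.3 says only "The summary of the SAEs will be provided by pharmacovigilance".

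Three protocol passages decide who stays under observation for toxicity:

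- Section IX ends study treatment for, among other reasons, "Disease progression (hepatic, extra-hepatic, clinical") and "Death of the patient".
- Section VIII.2: "After hepatic progression, the clinical, biological and morphological monitoring of the patient will be left to the investigator's discretion".
- Section XI asks for serious adverse events "that occur during treatment and within 30 days of the last treatment administration"; later ones are reported only if considered related.

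**The concern.** There are two linked problems.

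First, an analysis that the protocol places among its main analyses is absent from the SAP, and no reason is recorded. Tolerance over the 24 months of treatment is a secondary objective. Without a time-to-onset analysis, the report cannot show whether severe toxicity comes early or accumulates.

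Second, restoring the protocol sentence unchanged would bring in a bias. A patient who dies of another cause before any grade 3–5 toxicity can no longer have one. Kaplan-Meier censors that patient and so treats the later risk as still open. The complement of the curve is then higher than the proportion of patients who actually have severe toxicity. The same applies to patients who stop everolimus at progression, if the target is toxicity on treatment and they are censored at the stop.

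**Working it through.** **Inputs from the documents.** The documents give no figure for time to toxicity, so there is none to reproduce. SAP 5.5 gives 24-month event-free rates of 35% (null) and 50% (expected). The stated design reproduces with them: at least 31 successes of 68 gives an exact one-sided alpha of 4.6% and power of 80.2%, and 68/0.95 = 71.6, rounded up to 72. This confirms only that the rates are read correctly.

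**Assumptions.** Hazards are constant over 24 months. 1-KM for grade 3–5 toxicity is 20%, 40% or 60%. For death alone, 24-month survival is 90%, 80% or 70%. The documents state none of these.

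**Formulas.** Let a = −ln(1 − [1-KM]) be the cumulative toxicity hazard at 24 months, and b = −ln(S) the cumulative competing hazard, with S the event-free rate for the competing event. Then

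cumulative incidence = a/(a+b) × (1 − e^−(a+b)).

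Example with 1-KM = 40% and S = 50%: a = 0.511, b = 0.693, a+b = 1.204, e^−1.204 = 0.6 × 0.5 = 0.30. The result is 0.511/1.204 × 0.70 = 29.7%.

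**Results: cumulative incidence at 24 months**

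| Competing event | 1-KM 20% | 1-KM 40% | 1-KM 60% |
|---|---|---|---|
| Progression or death, S = 35% | 12.6% | 25.9% | 40.1% |
| Progression or death, S = 50% | 14.6% | 29.7% | 45.5% |
| Death only, S = 90% | 19.0% | 38.1% | 57.4% |
| Death only, S = 80% | 18.0% | 36.2% | 54.7% |
| Death only, S = 70% | 16.9% | 34.2% | 51.8% |

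The excess of 1-KM is 5.4 to 19.9 points in the first two rows and 1.0 to 8.2 points in the last three.

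**Early toxicity.** Suppose that all toxicity falls in the first 3 months. The competing hazard then acts only for 3/24 of the period, so b is replaced by b/8. With 1-KM = 40%, the cumulative incidence is 37.7% (S = 35%) or 38.5% (S = 50%). Over 1-KM of 20–60% and S of 35%, 50%, 80% and 90%, the excess is 0.1 to 3.2 points.

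**Low toxicity.** The only grade 3–4 figure in the documents is the less than 7% that Protocol XIII reports for a cited phase III trial. If 7% is taken as 1-KM, the cumulative incidence is about 4.4% (S = 35%) or 5.1% (S = 50%), an excess of 2 to 3 points.

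**The SAP counts.** With no loss to follow-up, the Aalen-Johansen estimate at the end of the period equals the crude proportion. Take the worked example and assume 5% lost, borrowing the allowance in SAP 5.5. The added hazard is −ln(0.95) = 0.051, and the crude proportion is 0.511/1.255 × (1 − 0.6 × 0.5 × 0.95) = 29.1%, against 29.7%. The counts are about 0.6 points from the target at 24 months.

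**The case against.** The strongest reply is that little is lost. Since the SAP drops the Kaplan-Meier curve, its bias cannot reach results produced under the SAP. Protocol XII.2 lists how tolerance will be assessed (treatment duration and doses, graded toxicities, serious events, WHO index), and time to onset is not on that list. The SAP covers those items in 7.6.2 to 7.6.5 and adds procedure complications in 7.6.1. This stands as a limit on importance. It does not remove the conflict, because XII.3 plans the analysis in so many words.

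Three stronger readings are tempting, and the documents do not support them.

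- A reader might infer that the maximum-grade counts mislead because many patients stop before 24 months. They do not. Counting a patient who stopped without severe toxicity as not having had it is what a competing-risk estimate also does, and the two nearly agree at 24 months. The counts cannot give the proportion at earlier times.
- A reader might infer that the protocol censors at progression. It states no censoring rule. Progression competes only if the target is on-treatment toxicity, which neither document defines. Kaplan-Meier censored at treatment stop can also be read as risk while treatment continues, which is a different question. Toxic deaths are grade 5 and count as events.
- A reader might take a gap such as 40% against 30% as the expected bias. It is one scenario with an assumed toxicity level and constant hazards.

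**Conclusion.** The point holds in a limited form. The main defect is the unexplained omission: Protocol XII.3 plans the analysis and the SAP does not contain it. The second defect matters only if the protocol analysis is run. 1-KM would then exceed the incidence of severe toxicity whenever deaths from other causes come first, and would exceed on-treatment incidence by more if stops at progression are censored.

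The direction follows from the method. The size does not follow from the documents, which give neither the timing of toxicity nor an overall survival rate; the ranges calculated above are illustrative. The primary endpoint and its decision rule are unaffected.

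**What to change.** In SAP 7.6.4, before the database is frozen (SAP 7.1.2), add the Aalen-Johansen cumulative incidence of first grade 3–5 toxicity, from first everolimus dose, in the safety population. Give 95% intervals at fixed times, for example 3, 6, 12 and 24 months. Treat death without such toxicity as a competing event. State the target: if it is on-treatment toxicity, also treat permanent everolimus stop for another reason, plus the 30-day window, as competing. Amend the sentence in Protocol XII.3 to match, and keep the counts in 7.6.4. If the sponsor prefers to drop the analysis, the SAP should record why.

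Two inconsistencies should be reconciled at the same time, because they affect the risk set and the onset dates. The tolerability population requires a dose of the treatments in Protocol XII.3 but a dose of everolimus in the SAP definition of the tolerance population (SP). Toxicities are collected at monthly visits according to Protocol XII.2, but scheduled visits are every 3 months in VIII.1.

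The cost is one SAP paragraph, one protocol sentence and standard code. Onset dates are needed, but the protocol's own analysis already required them.

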At the end of the trial, the observation book will be kept for 15 years by the investigator.

COMPUTER SUPPORT

In accordance with the text of the law n° 78-17 of January 6, 1978 modified by the law of August 9, 2004, relating to data processing, files and freedoms, the data of the trial will be recorded in a data bank of the Center of Randomization and Management Analysis of the FFCD, with the exception of the elements relating to the identity of the patients.

DATA PROCESSING

The FFCD's Center for Randomization, Management and Analysis (CRGA) will be responsible for data management and analysis.

MONITORING, QUALITY ASSURANCE AND INSPECTIONS BY AUTHORITIES

The investigator agrees in advance that the records of the patients included in the trial may be consulted by a person mandated by the FFCD and/or by the health authorities to conduct an audit. On-site visits to the files, scheduled after agreement by the investigator, may take place during or after the period of inclusion in the trial

This protocol will be monitored by the FFCD's mobile ARCs.

XV. PUBLICATION RULES

They shall be in accordance with those established by the FFCD (Appendix 8).

XVI. APPENDICES

3.1 Rationale for the study

Neuroendocrine tumors (NETs) are a heterogeneous group of rare tumors (estimated prevalence between 0.4 and 1 per 100,000 population per year).

Treatment of digestive endocrine tumors

There are numerous therapeutic options and the choice of treatment depends essentially on the location of the primary tumor, the stage of extension and the tumor's evolution. In all cases, the decision must be taken after multidisciplinary discussion. Symptomatic management of hormonal hypersecretion is imperative. Surgical removal of the primary tumor is usually recommended. In the case of well-differentiated NETs with little progression, initial surveillance may be proposed with an evaluation of the tumor's evolution. If the tumor is slowly progressive (tumor stability without new localization), surveillance, possibly associated with treatment with somatostatin analogues, may be proposed. If the tumor is progressive (morphological progression or new metastatic sites), antitumor treatment should be considered. In the case of NET of the digestive tract, which is not very chemosensitive, (chemo)embolization in case of isolated or predominant liver metastases is often the preferred option.

Place of (chemo)embolization

The principle of intra-arterial chemoembolization is to combine intra-arterial hepatic chemotherapy with embolization. As metastases are mainly vascularized by the arterial route, this approach allows to induce a targeted anoxia. Chemoembolization is effective in controlling clinical manifestations related to hormonal hypersecretion. The ENETS-01 trial, the only prospective randomized trial comparing embolization and chemoembolization (26 patients included), showed no difference in progression-free survival at 24 months between the chemoembolization (38%) and embolization (44%) groups. In the MD Anderson study (81 patients), the 24-month progression-free survival rate was 35%. In a French study (67 patients), the 24-month progression-free survival rate was about 35%.

Rationale for antiangiogenic therapy after (chemo)embolization

Digestive NETs are characterized by their hypervasculature. Tumor endocrine cells secrete excess VEGF which is likely to play an important role in the angiogenic process associated with endocrine tumorogenesis. Embolization stimulates angiogenesis with an increase in circulating VEGF levels and the main mechanism associated with a progressive recovery after (chemo)embolization is tumor revascularization from collateral vessels. Therefore, treatment with antiangiogenic action after (chemo)embolization could improve tumor control.

Everolimus

Inhibitors of the mTOR pathway have antiangiogenic activity, which explains in part their antitumor effect. In the phase II study by Yao *et al.*, the everolimus dose of 10 mg was retained for further development. Only the phase III RADIANT II study concerned NET of the digestive tract. This study randomized 430 patients between everolimus (10 mg/d) and placebo, combined in both arms with octreotide LP30mg/28d. Progression-free survival was 16.4 months in the everolimus arm versus 11.3 months in the placebo arm (HR = 0.77; 95% CI = 0.59-1.00; *p* NS) on centralized review. The center-read analysis (12.0 months *versus*

8.6 months, HR = 0.78; 95% CI = 0.62-0.98; p S) supported the superiority of everolimus with a very acceptable safety profile.

